6.5. Vaccination holding rules

Safety holding rules for each subject will apply throughout the study period until interim safety analysis (V4). Vaccination of further study subjects in the consecutive study phase will not occur until a safety review has been conducted by the DSMB and only by approval a holding rule can be resolved. If a holding rule is activated, the PI will inform the Sponsor within 48 hours. The Sponsor will inform the responsible authorities (PEI and EC).

If the DSMB permits the resumption of injections, a formal request with pertinent data must be submitted to ECs and PEI. The discontinuation of a holding rule should be communicated to all entities in the same manner and timeframe as described above.

The DSMB safety review will consider:

- The relationship of the AE or SAE to the vaccine or other possible causes of the event.
- If appropriate, additional screening or laboratory testing for other volunteers to identify those who may develop similar symptoms and alterations to the current informed consent form will be discussed.

All injected volunteers will be followed for safety until resolution or stabilization (if determined to be chronic sequelae) of their AE.

The holding rules are as follow:

Protocol		
Protocol code and Short Title:	P-pVAC-SARS-CoV-2	Date/Version:08.03.2021/V1.4

- **Solicited local ADRs:** If more than 30% of injections are followed by Grade ≥ 3 solicited swelling or pain or Grade 4 redness (first occurrence at any time after vaccination) and persisting at Grade 3 (swelling or pain)/4 (redness) for > 48 h to maximum 72 hours depending upon symptom severity and kinetics.
- **Solicited systemic AEs:** If more than 25% of injections are followed by Grade 3 solicited systemic AE beginning within 3 days after study injection (day of injection and 2 subsequent days) and persisting at Grade ≥ 3 for > 48 h to maximum 72 hours depending upon symptom severity and kinetics.
- **Unsolicited AEs:** If more than 25% of volunteers develop a Grade ≥ 3 unsolicited AE (including laboratory AE and physical observations) that is considered probably or definitely related to injection and persists at Grade 3 for > 48 to maximum 72 hours depending upon symptom severity and kinetics.
- A suspected unexpected serious adverse drug reaction (SUSAR) occurs that is life-threatening or results in death.

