9.1.2. Adverse Drug Reaction

An Adverse Drug Reaction (adverse reaction: undesirable effect) is a response to a medicinal product which is noxious and unintended. Adverse reactions may arise from use of the product within or outside terms of the marketing authorisation or from occupational exposure. Use

Protocol		
Protocol code and Short Title:	P-pVAC-SARS-CoV-2	Date/Version:08.03.2021/V1.4

outside the marketing authorisation includes off-label use, overdose, misuse, abuse and medication errors.

An unexpected Adverse Drug Reaction (ADR) is a reaction which nature or severity is not consistent with the applicable product information available for the IMP.

Expected ADRs are listed in the appropriate reference documents, e.g. Investigator's Brochures; and below:

A solicited AE/ADR is a predetermined event, which may reflect safety concerns related to the investigational product and is, at least for the local solicited AEs, expected. The solicited ADR/AEs (local and systemic) for this study include:

Local solicited ADRs:

- Swelling at site of injection
- Erythema at site of injection
- Pain or itching at site of injection
- Formation of granuloma at the injection site
- Superficial skin ulceration

Systemic solicited AEs:

- Fever
- Chills
- Myalgia (described to the subject as generalized muscle aches)
- Arthralgia (described to the subject as generalized joint aches)
- Fatigue
- Headache
- Gastrointestinal symptoms (loss of appetite, nausea, vomiting, abdominal pain, and/or diarrhoea)

A grading for severity of ADRs can be found in appendix 14.5 as guidance.

9.1.3. ***Expectedness***

An 'unexpected' adverse event is one the nature or severity of which is not consistent with the applicable product information, e.g. Investigator's Brochure (IB). Furthermore, reports which

add significant information on specificity or severity of a known adverse reaction are counted as 'unexpected' events.

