9.3.2. Assessment of Severity and Causality

The investigator will also provide an assessment of the severity of the event according to CTCAE criteria (Version 5.0) and causal relationship between the event and each of the investigational products or trial procedures.

AEs and SAEs should be evaluated for severity according to the following scale:

- Grade 1 Mild; asymptomatic or mild symptoms; clinical or diagnostic observations only; intervention not indicated.
- Grade 2 Moderate; minimal, local or noninvasive intervention indicated; limiting age-appropriate instrumental Activities of Daily Living (ADL).
- Grade 3 Severe or medically significant but not immediately life-threatening; hospitalization or prolongation of hospitalization indicated; disabling; limiting self care ADL.
- Grade 4 Life-threatening consequences; urgent intervention indicated.
- Grade 5 Death related to AE.

The investigator must determine the causal relationship between the administration of IMP and the occurrence of an AE/SAE as defined below:

Related: There is a reasonable possibility that the SAE may be related to the IMP (e.g. favorable temporal relationship, positive dechallenge: symptoms are receding when IMP is withdrawn or the dose reduced, positive rechallenge: symptoms are reappearing when the IMP is reintroduced or the full dose is re-administered)

Not Related: There is no reasonable possibility that the SAE is related to the IMP (e.g. there is a plausible alternative cause for the SAE that better explains the occurrence of the SAE)

Outcome of AEs

The outcome of an AE at the time of the last observation will be classified as:

Recovered/ resolved	All signs and symptoms of an AE disappeared without any sequels at the time of the last interrogation.
Recovering/ resolving	The intensity of signs and symptoms has been diminishing and/ or their clinical pattern has been changing up to the time of the last interrogation in a way typical for its resolution.
Not recovered/ not resolved	Signs and symptoms of an AE are mostly unchanged at the time of the last interrogation.

Protocol		
Protocol code and Short Title:	P-pVAC-SARS-CoV-2	Date/Version:08.03.2021/V1.4

Recovered/ resolved with sequel	Actual signs and symptoms of an AE disappeared but there are sequels related to the AE.
Fatal	Resulting in death. If there are more than one AE, only the AE leading to death (possibly related) will be characterized as 'fatal'.

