14.5. Intensity of solicited and unsolicited local and systemic adverse events

Local solicited AEs	CTCAE Term	Grade 0 Normal	Grade 1 Mild	Grade 2 Moderate	Grade 3 Severe	Grade 4 Potentially life-threatening
Erythema	Injection site reaction	< 25 mm	25-50mm Tenderness with or without associated symptoms (e.g., warmth, erythema, itching)	51-100mm Pain; lipodystrophy; edema; phlebitis	> 100mm Ulceration or necrosis; severe tissue damage; operative intervention indicated	Life-threatening consequences; urgent intervention indicated
Swelling		< 25 mm	25-50 mm and does not interfere with activity	> 50 mm or interferes with activity	Prevents daily activity	Necrosis
Pain	Injection site reaction	None	Tenderness with or without associated symptoms (e.g., warmth, erythema, itching) Does not interfere with activity	Pain; lipodystrophy; edema; phlebitis Interferes with activity	Ulceration or necrosis; severe tissue damage; operative intervention indicated Prevents daily activity	Life-threatening consequences; urgent intervention indicated Emergency room visit or hospitalization

Protocol

Protocol code and Short Title:

P-pVAC-SARS-CoV-2

Date/Version:08.03.2021/V1.4

Systemic solicited AEs	CTCAE Term	Grade 0	Grade 1	Grade 2	Grade 3	Grade 4
Fever		None	38.0° - 39.0°C	≥ 39.0° - 40.0°C	≥ 40.0°C for ≤ 24 hours	≥ 40.0°C for ≥ 24 hours
Chills		None	Mild sensation of cold; shivering; chattering of teeth	Moderate tremor of the entire body; narcotics indicated	Severe or prolonged, not responsive to narcotics	-
Myalgia (described to the subject as generalized muscle aches)		None	Mild pain	Moderate pain; limiting instrumental ADL	Severe pain; limiting self care ADL	-
Arthralgia (described to the subject as generalized joint aches)			Mild pain	Moderate pain; limiting instrumental ADL	Severe pain; limiting self care ADL	-
Fatigue			Fatigue relieved by rest	Fatigue not relieved by rest; limiting instrumental ADL	Fatigue not relieved by rest, limiting self care ADL	-
Headache		None	Mild pain	Moderate pain; limiting instrumental ADL	Severe pain; limiting self care ADL	-
Gastrointestinal symptoms (nausea, vomiting, abdominal pain, and/or diarrhea)	nausea	None	Loss of appetite without alteration in eating habits	Oral intake decreased without significant weight loss, dehydration or malnutrition	Inadequate oral caloric or fluid intake; tube feeding, TPN, or hospitalization indicated	-

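### Holding rules in 6.5: the unsolicited hold uses causality levels that 9.3.2 does not define, and non-serious Grade 3 superficial ulceration counts only if it is graded as pain

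*Supplement*

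**What the plan says.** All references are to protocol V1.4.

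**Unsolicited hold (6.5).** It is reached when more than 25% of volunteers have an unsolicited event of Grade 3 or higher "that is considered probably or definitely related to injection and persists at Grade 3" for more than 48 hours.

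**Causality scale (9.3.2).** The investigator must classify every AE and SAE at one of two levels. Related means: "There is a reasonable possibility that the SAE may be related to the IMP". Not Related means: "There is no reasonable possibility that the SAE is related to the IMP".

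**Local hold (6.5).** It begins "If more than 30% of injections are followed by" and counts events of Grade 3 or higher as "solicited swelling or pain or Grade 4 redness", again with persistence beyond 48 hours. Swelling and pain thus count from Grade 3, redness only at Grade 4. No other local reaction is named.

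**Solicited list (9.1.2).** The local solicited reactions include "Superficial skin ulceration" as an item of its own. On grading, the section says: "A grading for severity of ADRs can be found in appendix 14.5 as guidance".

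**Grading table (Appendix 14.5).** There is no ulceration row. The descriptor "Ulceration or necrosis; severe tissue damage; operative intervention indicated" stands at Grade 3 in both the Erythema row and the Pain row.

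**The concern.** A percentage hold is useful only if two people with the same data reach the same count. Here two of the three percentage holds may fail that test. One filters on probable or definite causality, terms that belong to a graded scale, while the protocol asks the investigator for a yes-or-no judgement. The other depends on which row of the appendix is used to grade an ulcer.

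These holds are the numeric pause rules that operate below the level of an SAE or of a fatal or life-threatening SUSAR. If their counts are ambiguous, the pause rests on discretion in the situation where a preset rule was meant to replace it. Ulceration is not a remote event for this product: section 5.7.2.1 reports it in 8% of the 12 Part I volunteers.

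**Working it through.** **Plan's own figures.** The holding rules state limits but no operating characteristics, so there is nothing in them to reproduce. The sample-size figures in 8.1.1 do reproduce: power 1 − 0.95^33 = 0.816, actual level 1 − 0.9999^33 = 0.0033, enrolment 33/(1 − 0.075) = 35.7, rounded up to 36. They do not depend on the present point.

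**Step 1: causality.** Let R be the number of volunteers with a qualifying event classed as Related, and D the number whose event is probably or definitely related. Related covers any reasonable possibility, so 0 ≤ D ≤ R. The 9.3.2 scale gives R. Nothing in the protocol gives D. Section 9.3.7 uses a further phrase for SUSARs, to set aside events that are ruled out as related, but it defines no probable or definite level.

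**Step 2: when that matters.** The smallest count k with k/n strictly above the limit is shown below. Section 6.5 does not say whether the percentages are per part or cumulative, so both are shown as assumptions.

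| n | more than 25% (unsolicited) | more than 30% (local) |
|---|---|---|
| 12 (Part I) | 4 (33.3%) | 4 (33.3%) |
| 24 (Part II) | 7 (29.2%) | 8 (33.3%) |
| 36 (both) | 10 (27.8%) | 11 (30.6%) |

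If R is below k, no reading of the rule triggers the hold. If R is at or above k, the answer depends on D. With 7 Related cases among 24, for example, the hold is reached if all 7 qualify and not reached if any one is judged only possibly related.

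**Step 3: ulceration.** Take a non-serious, superficial Grade 3 ulcer that lasts more than 48 hours.

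| How it is graded | Unsolicited hold | Local hold |
|---|---|---|
| Pain, Grade 3 | no (solicited) | counted |
| Erythema, Grade 3 | no (solicited) | not counted (Grade 4 only) |
| Its own solicited term | no (solicited) | not counted (not named) |

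The same lesion adds 1 or 0 to the count. On the second and third lines, even 24 of 24 such ulcers would not reach a percentage hold.

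**Step 4: Part I.** 8% of 12 is 0.96, so 1 volunteer: 1/12 = 8.3%, exact 95% interval 0.2% to 38%.

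**Step 5: what adding ulceration would do.** The chance that Grade 3 or higher ulceration alone reaches the local hold in Part II is P(X ≥ 8) for a binomial with n = 24. The true rate is not known, so it is assumed over a range.

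| Assumed rate | P(hold reached) |
|---|---|
| 8.3% | below 0.001 |
| 20% | 0.089 |
| 30% | 0.435 |
| 50% | 0.968 |

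The 8.3% line uses the Part I rate of ulceration of any grade, so the rate at Grade 3 or higher can only be equal or lower in that sample.

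**The case against.** **Other rules catch the worse ulcers.** This stands, and it sets the limits of the point. A reader might infer that no ulceration of Grade 3 or above is held unless it is called pain. The documents do not support that. Grade 4 redness counts, and necrosis is Grade 4 swelling, which also counts. Only superficial ulceration is solicited, and the Grade 3 descriptor, with severe tissue damage, can describe something deeper; such a lesion could be classed as unsolicited and come under the 25% hold. A serious, vaccine-associated ulcer reaches the one-SAE stopping rule in 8.6.

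**The site may record finer causality levels.** Section 9.3.1 allows further instructions in the investigator file and the case report form, and neither is shown. So it cannot be said that the site does not collect the category, only that the protocol does not define it. Because R is an upper bound on D, the mismatch also does not hide events from the DSMB, which examines relatedness whenever a hold is reviewed.

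**Discretion remains, and little vaccination is left to pause.** The DSMB is told of all safety-relevant events (9.4.1) and can meet at any time (1.4). Sections 6.8 and 8.6 allow termination for unacceptable toxicity. Part I is complete, and Part II is the last part, with its volunteers vaccinated in parallel. This limits the practical effect, but it does not make the two rules countable.

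**Related lowers the bar as well as clarifying it.** True. Defining probable and definite in 9.3.2 would also cure the mismatch, at the price of a longer scale for every event.

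**Conclusion.** The point holds in two parts.

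- The unsolicited hold cannot be evaluated on the only causality scale that the protocol defines. The ambiguity affects the decision once Related cases reach 4 of 12, 7 of 24 or 10 of 36, depending on the denominator assumed.
- Non-serious Grade 3 superficial ulceration counts toward the local hold in full under Pain and not at all under Erythema or its own term. This rests on treating it as solicited, as 9.1.2 does, and on using the Appendix 14.5 rows, which are offered as guidance.

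Three further inferences are not supported. First, no Part I hold was missed: there was one ulceration against the 4 of 12 needed per part, section 1.1.5.1 describes these local events as mild, and the lesion is not described closely enough to dispute that. Second, the one-SAE stopping rule is not left without an attribution: 8.2 acts on reports made under 9.3.1, and those carry the investigator's causality assessment. What happens if the second assessor disagrees is unstated, but that is missing detail, not an error. Third, the silence in 6.5 on the denominator is likewise a matter for clarification. Granuloma is an expected and intended reaction, and its absence from the local hold is no fault.

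This is a wording repair to two safety rules, worth making but with limited practical effect.

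**What to change.** 1. In the unsolicited hold in 6.5, replace the probable-or-definite condition with Related as defined in 9.3.2.
2. Add injection-site ulceration of Grade 3 or higher to the solicited local hold in 6.5.
3. Give ulceration its own row in Appendix 14.5, so that its grade no longer depends on choosing between the Erythema and Pain rows.

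The cost is amendment wording in one section and one table row. Both holds become somewhat easier to reach, so a precautionary pause is slightly more likely. For ulceration alone in Part II that added chance is negligible near the Part I rate and becomes material only if severe ulceration is common, which is when a pause would be wanted.

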6.6. Premature termination of clinical trial for a trial subject

Reasons for premature termination of trial for an individual trial subject are:

1. Death
2. Withdrawal of consent
3. Volunteer lost to follow-up
4. For women, in case of pregnancy

The PI decides about withdrawal of subjects from trial treatment in case of occurrence of criteria mentioned above. In all cases, the reason for withdrawal must be recorded in the CRF and in the subject's medical records. In case of withdrawal of a subject at his/ her own request, the reason should be determined and documented.

All examinations scheduled for the last trial day will be performed and documented as far as possible, subject to consent of the volunteer. Subjects will enter the regular follow-up of the trial, unless the subject has withdrawn his/her consent to any further study-related procedure. If a subject is withdrawn from all trial-related procedures (including follow-up visits) e.g. at his/her own request, this will not result in any disadvantages for the volunteer.

Protocol		
Protocol code and Short Title:	P-pVAC-SARS-CoV-2	Date/Version:08.03.2021/V1.4

All ongoing Adverse Events (AEs)/ Serious Adverse Events (SAEs) of withdrawn subjects have to be followed-up until no more signs and symptoms are verifiable or the subject is on stable condition.

Premature termination should be avoided. In case of a premature termination of study, reasons/circumstances and if applicable the final status have to be documented. If volunteers do not withdraw the consent for further follow-up, they should be followed-up as planned.

6.7. Premature closure of a trial site

Premature closure of a trial site has to be considered if:

- The recruitment rate is not sufficient
- The conduct of the study is not compliant with the protocol or the legal regulations, or
- The data quality is not sufficient

The premature closure of a site will be decided by the sponsor.

Site principal investigators may terminate his/her participation in the study. If this occurs they should provide a written statement of the reasons for terminating participation and must provide the sponsor with all available and up-to-date study data.

The sponsor may also decide to terminate participation of an investigator or study centre for the following reasons:

- Breach of agreement
- Serious non-compliance to protocol or the legal regulations
- Insufficient volunteer recruitment

If a participating center closes, or is closed, prior to termination of the whole trial, the sponsor expects that data from volunteers already entered into the trial will be reported as per protocol. Details on further treatment and follow-up of volunteers on study have to be discussed with the site principal investigator.

6.8. Premature termination of the trial

The trial may be prematurely terminated, if in the opinion of the sponsor and coordinating investigator, there is sufficient reasonable cause. Written notification documenting the reason for study termination will be provided to the investigators.

In case of the following situations a premature termination of the trial has to be considered:

Protocol		
Protocol code and Short Title:	P-pVAC-SARS-CoV-2	Date/Version:08.03.2021/V1.4

- Observation of one SAE associated with administration of CoVac-1 (Statistical Stopping rule of the study)
- Serious adverse drug reactions / not justifiable toxicity
- Substantial changes in risk-benefit considerations
- New insights from other trials
- Insufficient efficacy
- Insufficient recruitment rate

The DSMB will monitor the study conduct and the safety aspects of the trial on a regular basis, and will give recommendations to the coordinating investigator/ the sponsor whether to stop the trial or to change the trial protocol. The sponsor will then decide on the actions to be taken. According to the German drug law (§42a), the trial may be suspended or prematurely terminated by decision of the competent authority (PEI).

6.9. Follow Up

Volunteers will be followed for up to 4 months after EOSf. Thereafter patients may be contacted by phone call/e-mail to assess infection with SARS-CoV-2.

6.10. End of Study for Subjects

The end of Study for a subject enrolled in this trial is defined as the last study visit.

7. Quality control and Quality assurance

7.1. Risk-based approach

During protocol development, processes and data that are critical to ensure human subject protection and the reliability of trial results were identified.

The identified risks were evaluated against existing risk controls by considering:

- The likelihood of errors occurring
- The extent to which such errors would be detectable
- The impact of such errors on human subject protection and reliability of trial results.

In case of unacceptable risks, risk reduction activities were defined and incorporated e.g. in the protocol, monitoring plan and agreements.

Results will be communicated to those who are involved in or affected by such activities.

The sponsor periodically reviews risk control measures to ascertain whether the implemented activities remain effective and relevant, taking into account emerging knowledge and experience.

7.2. Monitoring

Monitoring for this study is provided by the *Zentrum für Klinische Studien Tuebingen* (ZKS Tuebingen). The monitoring will be conducted according to *ZKS Tuebingen Internal Standard Operating Procedures (SOPs)* and a dedicated monitoring manual for the study. The monitoring timelines include, for all centres, initiation visit, regular monitor visits during the course of the trial as well as a close out visit. Usually, monitoring will end with the last visit after full documentation of the last volunteer enrolled (close out visit). All investigators agree that the monitors regularly visit the trial site, assure that the monitors will receive appropriate support in their activities and will have access to all trial-related documents.

The aims of the monitoring visits are as follows:

- Check informed consent documents
- Monitor trial subject safety (occurrence and documentation/reporting of Serious Adverse Events (SAEs) and Adverse Events (AEs)).
- Check completeness and accuracy of entries on the CRFs.

Protocol		
Protocol code and Short Title:	P-pVAC-SARS-CoV-2	Date/Version:08.03.2021/V1.4

- Validate entries on the CRFs against those in the source documents (source data verification (SDV)).
- Check the Drug Account
- Check the storage conditions of the IMP
- Evaluate the progress of the trial
- Evaluate compliance with the trial protocol
- Assess whether the trial is being performed according to GCP at the trial site
- Discuss with the investigator aspects of trial conduct and any deficiencies found
- A monitoring visit report is prepared for each visit describing the progress of the clinical trial and any problems

